4.3.3 Seven Day Safety Follow up (visit 3)

The Investigator will contact the patient seven days after the initial cystoscopy/TURBT to record complications, adverse events and concomitant medication or procedures. This contact may be by telephone.

4.3.4 Unplanned Visits

Temporary visits should be made based on clinical needs. Corresponding laboratory abnormalities and adverse events with significant clinical use should be recorded in the CRF and original data.

Study Number: YHCT-HEX-B1

5. Investigational Medicinal Product and Device

5.1 Investigational Drug

5.1.1 Drug name, Dosage Form and Specification

Name:	Hexvix (hexaminolevulinate hydrochloride for intravesical solution)		
Dosage Form:	Powder		
Specification:	Hexvix is supplied as a kit containing a 10 mL glass vial containing 85 mg powder of Hexvix (hexaminolevulinate hydrochloride, HAL HCl) for Intravesical Solution, and a prefilled syringe containing 50 mL solvent for Hexvix.		
Administration:	The HAL solution is prepared by reconstituting 85 mg HAL HCL with 50 mL solvent. Instillation of the Hexvix solution into the bladder through a catheter, retaining in bladder for 1 to 3 hours before the cystoscopy. Detailed administration sees drug instructions.		
Storage:	Hexvix Kit for Intravesical Solution should be stored at 10-30°C. Detailed storage see the drug instructions.		

5.1.2 Administration

Investigational drug: Hexvix (hexaminolevulinate hydrochloride for intravesical solution), bladder instillation, single administration. The HAL solution is prepared by reconstituting 85 mg HAL HCL with 50 mL solvent. Instillation of the HAL solution into the bladder through a catheter, retaining in bladder for 1 hours before the cystoscopy. Detailed administration sees drug instructions.

5.1.3 Packaging

The sponsor or delegate CRO will design the label for investigational drug and perform packaging and labeling according to Good clinical practice (GCP) and applicable regulations.

5.1.4 Labelling

The content of the drug label at least includes the followings:

- Clinical trial drug name, strength and dosage form (For clinical trial use only)
- Sponsor
- Protocol number
- Storage conditions
- Expiry date
- Administration method
- Batch number

5.1.5 Drug Distribution, Recording and Recover

Drugs used in this trial are provided and processed according to with GCP regulations. Special personnel from study site are responsible for receipt, inventory management, medication for each subject, drug recover and maintenance of related records. Study drugs must be distributed in

Study Number: YHCT-HEX-B1

accordance with the requirements of the protocol. Study drugs are provided by the sponsor in free of charge and distributed to each study site, kept and distributed by special personnel from study site. The "Investigational Drug Registration Form" should be filled in and confirmed by the drug administrator and investigator each time the drug is distributed and recovered.

All investigational drugs provided by the sponsor can only be used in this clinical study, and not for purposes out of this protocol. The investigator must promise not to provide the investigational drug to anyone unrelated to this trial. The investigator is required to keep proper records of all investigational drugs distributed, including the date, quantity, and which subjects used.

Un-used study drugs must be returned to the sponsor or destroyed in accordance with the procedures of the relevant regulatory in effect.

5.2 Photodynamic Diagnostic Equipment (PDD) System

The PDD system used in clinical research, namely Richard Wolf PDD system (System blue), is a complete cystoscopy equipment developed for white light and blue light cystoscopy. The system includes any of the following:

- Camera controller, Camera head, Light source, Light cable
- PANOVIEW blue telescopes

ENDOLIGHT LED blue light source and system blue:

The ENDOLIGHT LED blue light source is intended to be used for PDD. The system enables to use of a white light mode, and a blue light mode enabling fluorescence excitation for PDD.

For the application for PDD, the ENDOLIGHT LED blue light source is equipped with two separate LEDs, one for the "white light mode" with an emission spectrum covering almost the entire visible light range and one for the "blue light mode" with peak emission at about 410 nm. This is used to induce and observe tissue fluorescence after hexvix administration. The different LEDs are activated independently from each other, depending on the desired mode of operation, with only one of the LEDs can be operated at once.

The diagnostic approach is selected and configured using the camera controller in the camera menu, a process that normally takes place once at the start of the application. The user can switch between white light and blue light mode using a mode selection button on the light source, or a button on the camera head. Normally, a user switches between white light and blue light several times during an application.

The Richard Wolf PDD system (System blue) for optical diagnosis has been approved for marketing in the European Union and Japan. PDD system (System blue) has not yet been approved for marketing in China. In conjunction with the photosensitizer used and in blue light mode, the PDD system (System blue) respectively the blue light mode is used as an extension of the white light mode for improved detection of superficial bladder tumors. PDD system (System blue) is prohibited for:

- 1. The PDD system (System blue) must not be used in patients who are not suitable for white light endoscopy.
- 2. The following patient groups are not suitable for blue light mode:

Study Number: YHCT-HEX-B1

- Patients who were treated with chemotherapy or immune therapy within the previous six weeks;
- Patient with a florid infection of the urinary tract;
- Patients who already showed an immunological reaction to one of the photosensitizers used in photodynamic diagnostics.

Type no	Product description	Country	Certificate	Valid since
5525833	LOGIC HD PENDUAL CAMERA HEAD BLUE	EU	501,125	19.08.2016
		Japan	13B1X10183P00046	16.01.2019
5165001	LIGHT SOURCE LED BLUE	EU	900,056a	19.08.2016
		Japan	13B1X10183P00047	08.01.2019
8650514	TELESCOPE BLUE 0°Ø 4MM WL 298MM	EU	441,063e	20.01.2006
		Japan	303AIBZI00003000	16.03.2021
8654531	TELESCOPE BLUE 12% 4MM WL 298MM	EU	441,063e	20.01.2006
		Japan	303AIBZI00003000	16.03.2021
8654522	TELESCOPE BLUE 30% 4MM WL 299MM	EU	441,063e	20.01.2006
		Japan	303AIBZI00003000	16.03.2021
8650515	TELESCOPE BLUE 70% 4MM WL 303MM	EU	441,063e	20.01.2006
		Japan	303AIBZI00003000	16.03.2021

The light detection procedure involves irradiating the bladder wall with blue light. Due to the limited penetration of blue light in the tissue, the photoactivation of PAP only occurs on the surface of bladder wall. The light dose given by PDD system is small, and no complications are expected in rgards to light application in patients who undergo blue fluorescence cystoscopy [22].

The irradiance at the distal end of cystoscope is about 200 mW. Assuming that the typical light diagnostic procedure in the patient lasts about 30 minutes, a total light dose of 360 J is applied to the bladder wall. When uniformly distributed on the bladder wall (about 300 cm 2), a total light dose of about 1.2 J/cm 2 is applied. In a rat study [22], no or slight loss of healthy urothelium and no necrosis of urothelium and lamina propria were observed after perfusion of ALA (1%) and application of 50 J light dose (about 25 J/cm 2). Therefore, the light dose (1.2 J/cm 2) for human diagnostic purposes is not enough to cause any damage to urothelial cells in vivo.

System blue and its components (for PDD blue light cystoscopy) have been proved to have good clinical efficacy and safety in several studies [23-28]. The main risk associated with the application of System blue is the potential failure of cystoscopy examination due to device deficiencies. Due to the strict adherence to all standard design and production safety protocols, the possibility of a technical failure during cystoscopy with the System blue is extremely low. In addition, appropriate measures have been taken to minimize the risk to the study subjects, and if unrecoverable device deficiencies

Study Number: YHCT-HEX-B1

occurred in some or all components of the System blue during the trial, e.g ①In the case of blue light mode failure, subjects could still be examined by the investigator using the white light mode and resection can be performed in the white light mode; ②In the event of a malfunction of the System blue, the investigator can immediately withdraw the investigational device and do the examination and surgery with their standard equipment they use for all their patients diagnosed with bladder cancer.

Study Number: YHCT-HEX-B1

6. Treatment of Subjects

6.1 IMP

All eligible subjects well receive instillation of 50 mL Hexvix solution for 1hour

All eligible subjects well receive single administration (visit 2).

6.2 Concomitant Medication

Concomitant medications include any drugs (including prescription drugs, over-the-counter drugs, natural extracts, nutritional supplements, traditional Chinese medicines, etc.) used by the subject from signing the informed consent form (ICF) to the completion of the last visit specified in the flowchart. Note: There is no need to record normal saline. The medications used by subjects during the screening period are recorded as medication history. Any prescription drugs and over-the-counter drugs, herbal medicines, vitamins and nutritional supplements used by the subjects must be reviewed and approved by the investigators. Information on concomitant medications should be recorded in detail.

During the study period, symptomatic treatment drugs that will not affect the efficacy and safety of the study drug can be used in combination, and the medication should be specified in detail.

6.3 Compliance

The investigator must emphasize compliance to the subjects when they agree to the interview.

During the trial, if the subject's compliance is poor, the investigator should find out the reason, actively take corresponding measures (such as emphasizing the importance of protocol compliance to the subject), and fully record the non-compliance, the reason, and the corresponding measures taken.

Version 2.2 Date: Feb 6th, 2023

**Confidential*

**Confidential*

**Confidential*

Tenders

Confidential

Tenders

Confidential

Tenders

Study Number: YHCT-HEX-B1

7. Assessment of Efficacy

All efficacy endpoints assessments will be based on central pathology results, which will be used for statistical comparisons.

7.1 Primary Efficacy Endpoint

The primary efficacy endpoint of this study as below:

• The proportion of patients with histology-confirmed tumors (Ta, T1, or CIS) who have at least one such tumor found by Hexvix but not by white light cystoscopy.

7.2 Secondary Efficacy Endpoint

The secondary efficacy endpoint of this study as below:

- The proportion of patients with one or more CIS lesions detected with Hexvix blue light cystoscopy not by white light cystoscopy.
- The lesion detection rate of Hexvix blue light cystoscopy, compared to white light cystoscopy per lesion type (PUNLMP, CIS, Ta, T1, T2-T4).
- The proportion of false positive lesions detected with Hexvix blue light cystoscopy and white light cystoscopy.

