1.2 Drug Introduction

Hexaminolevulinate hydrochloride is approved in Europe under the brand name Hexvix for the following indication: "Hexvix blue light fluorescence cystoscopy is indicated as adjunct to standard white light cystoscopy to contribute to the diagnosis and management of bladder cancer in patients with known or high suspicion of bladder cancer". In the United States the product is approved under the brand name Cysview for the following indication: Cysview is an optical imaging agent indicated

Version 2.2 Date: Feb 6th, 2023

Study Number: YHCT-HEX-B1

for use in the cystoscopic detection of carcinoma of the bladder, including carcinoma in situ (CIS), among patients suspected or known to have lesion(s) on the basis of a prior cystoscopy, or in patients undergoing surveillance cystoscopy for carcinoma of the bladder.

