2.2 Secondary Objective

- Comparison of detection of patients with CIS lesions by Hexvix blue light cystoscopy and white light cystoscopy.
- Comparison of detection rates of bladder lesions of Hexvix blue light cystoscopy and white light cystoscopy per lesion type (PUNLMP, CIS, Ta, T1, T2-4).
- Comparison of the proportion of false positive lesions detected with Hexvix blue light cystoscopy and white light cystoscopy.
- Evaluation of safety of Hexvix in patients with bladder cancer.

Version 2.2 Date: Feb 6th, 2023

Study Number: YHCT-HEX-B1

3. Selection and Withdrawal of Subjects

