4.1 Study Type and Design Principle

A Prospective, within patient controlled multicenter study.

This study includes 3 regular visits: screening visit(-2w), cystoscopic examination (day 0), safety follow-up(1w). Study design as below:

[figure not shown]

Fig2. Study design

At the start of the study, a minimum of four subjects included at each center will be training subjects. These subjects will receive the Hexvix administration and undergo white and blue light cystoscopy with tumor resection as below. They will receive the same safety follow up as all the other included patients, after completing the safety follow-up for 1 week, the patients will be treated according to hospital's clinical routine by the Investigator. These patients are not part of the efficacy analyses.

To reduce possible bias in assessment of the objectives, a small number of subjects will be randomized to not continue with Hexvix blue light cystoscopy following white light cystoscopy.

Consented, eligible subjects (Visit 1) will be instilled with 50 mL Hexvix 8 mM solution for one hour. After bladder evacuation, the following procedure will be utilized to accomplish the cystoscopic examination of each subject:

1. Turn on the white light. Inspection of the bladder and mapping of all papillary lesions and flat and suspicious lesions seen under white light, record lesion number, size and location.

2. Randomization:

- a) If the patient is not randomized to undergo blue light mapping, proceed to step 3.
- b) If the patient is randomized to continue with blue light mapping, or subjects for investigator training procedure, then they will undergo blue light cystoscopy. Turn to the blue light. Inspection of the bladder and mapping of all papillary lesions and flat and suspicious lesions seen under blue light, record lesion number, size and location.
- 3. All papillary lesions detected will be resected using TURBT and all flat and suspicious lesions detected will be biopsied. The lesions resected and biopsied should be marked and pathologically examined separately. For patients randomized to undergo blue light cystoscopy and for training patients, the completeness of the resection should always be checked under blue light before finalizing the TURBT procedure until it is ensured that all lesions and

Study Number: YHCT-HEX-B1

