In general, false fluorescence from normal tissue will be weak and diffuse. The endothelium of blood vessels and inflamed areas may show false fluorescence, but fluorescence from neoplastic lesions will be more intense and usually well demarcated. To avoid false fluorescence and get a brighter picture, the endoscope should be held perpendicular and close to the bladder wall. Tangential light will give false fluorescence. Changing of fluorescence intensity when varying the observation angle indicates false fluorescence, as true fluorescence is persistent. A brighter picture will be achieved using a low magnification if a zoom lens is used. Bleeding will reduce the image brightness and good irrigation should be used. Photo bleaching, which is caused by destruction of the photosensitizer and leads to reduced fluorescence intensity, should be kept at a minimum by avoiding unnecessary delay during inspection and mapping of the bladder. Photo bleaching is normally not a problem during inspection and mapping of the bladder, but may be noticed during extensive use of fluorescence-guided resection. However, regeneration of fluorescence may be seen in areas kept 'in the dark' for a few minutes. To minimize photobleaching, the use of white light should be performed under the lowest possible light intensity. Viewing conditions may be altered by the presence of urine, and the bladder should therefore

Study Number: YHCT-HEX-B1

be adequately evacuated before starting the procedure together with proper irrigation during the examination. Please ensure that the bladder is sufficiently distended as a folded bladder wall may result in increased fluorescence

4) Biopsy/TURBT/Histology

Biopsies/TURBT will be obtained as part of the cystoscopic procedures. Perform biopsy and resection of all lesions and suspicious areas seen in blue light and white light. Both biopsied and resected tissue will be examined by the local pathologist, then evaluated by independent and blinded central pathologists. Central pathology results will be used as reference standard in the study efficacy endpoints.

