7.3 Central Pathology Evaluation

All efficacy endpoints assessment will be based on central pathology consensus panel results to reduce the difference between the pathological evaluations used in the efficacy analysis.

The WHO 2016 World Health Organization/International Society of Urologic Pathology consensus classification and the Union for International Cancer Prevention (UICC) 2017 8th edition of TNM classification for staging of bladder cancer will be used to grade and stage tumors. Two independent pathologists unaware of the diagnosis of the local pathologist and whether the biopsy came from a lesion seen in white light or blue light or both, provide a pathology diagnosis independently. If the two pathologists agree on the diagnosis, this is the final diagnosis. If they disagree, a third independent pathologist will make a diagnosis without knowing the diagnosis of the two first pathologists. If this diagnosis is in agreement with the diagnosis made by the one of the first pathologists, this result will be the final diagnosis. If they agree on a diagnosis, this will be the final consensus diagnosis. If they fail to reach agreement, this lesion will be excluded from the statistical analysis.

A histologically confirmed malignancy is a tumor staged/graded as CIS, Ta, T1 orT2-T 4 by the consensus panel. Lesions can be classified to PUNLMP, low grade and high grade.

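### The false positive endpoint gives one proportion per light, with no stated denominator and no figure for benign lesions sampled only because blue light was added

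*Combined protocol and SAP*

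**What the plan says.** The objective in section 2.2 is "Comparison of the proportion of false positive lesions detected with Hexvix blue light cystoscopy and white light cystoscopy". The matching endpoint in section 7.2 is "The proportion of false positive lesions detected with Hexvix blue light cystoscopy and white light cystoscopy". Neither section says what a false positive is, what the proportion is taken over, or whether lesions seen in only one light are reported separately.

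The design in section 4.1 is described as "A Prospective, within patient controlled multicenter study": the same bladder is mapped in white light and then, unless the patient is randomized out, in blue light. The sampling instruction in section 4.3.2.1 is "Perform biopsy and resection of all lesions and suspicious areas seen in blue light and white light". Section 7.3 blinds the central pathologists to "whether the biopsy came from a lesion seen in white light or blue light or both", so the plan recognises three classes of lesion.

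The primary endpoint (7.1) counts patients "who have at least one such tumor found by Hexvix but not by white light cystoscopy", and the first secondary endpoint does the same for CIS. The second secondary endpoint is a lesion detection rate for each light by lesion type, with PUNLMP among the types.

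Section 10.4.2.2 makes the secondary endpoints descriptive, with exact 95% intervals on the FAS and PPS. Where an interval rests on biopsy or TURBT data, it treats the specimens as independent.

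**The concern.** Section 1.2 quotes the European indication, in which blue light is "indicated as adjunct to standard white light cystoscopy". For an adjunct, the added cost in benign tissue is what is sampled because blue light was switched on and would not have been sampled otherwise. A proportion for each light does not isolate that quantity, because lesions seen in both lights can sit in both numerators and both denominators. The cost is foreseeable: section 4.3.2.1 warns that vessels and inflamed areas can fluoresce falsely.

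The population makes this relevant. Section 10.2 assumes 35% of subjects have bladder cancer, so about 65% would not. Those subjects cannot enter the mFAS, and benign biopsies taken from them appear among the efficacy endpoints mainly through this one.

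Two further gaps affect how the result is read. Lesions from one patient are treated as independent. And because a false positive is undefined, the place of PUNLMP is open: it is a lesion type to be detected in 7.2, but it is absent from the nearest reference text in 7.3, "A histologically confirmed malignancy is a tumor staged/graded as CIS, Ta, T1" (the sentence goes on to T2-T4 and no further).

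**Working it through.** **The plan's own figure.** The documents give no calculation for this endpoint. The only design calculation is for the primary endpoint, and it reproduces. With 94 patients and rejection at 16 or more, the exact one-sided type I error at 10% is 0.0239 and the power at 20% is 0.8006. Then 94 / (0.35 × 0.75) = 358.1, rounded up to 359, and 359 / 0.95 = 377.9, or about 380. Nothing below touches these numbers.

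**Assumptions.** The documents give no lesion counts, no overlap between lights and no false positive rates, so all lesion figures here are illustrative. The denominator is taken as the lesions seen by that light, which the plan does not state.

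**Formula when blue light re-finds every white-light lesion.** Let f_W be the white-light false positive proportion, f_b the proportion among blue-only lesions, and q the blue-only share of all blue-light lesions. The blue-light proportion is

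f_B = (1 − q) × f_W + q × f_b,

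so f_B − f_W = q × (f_b − f_W).

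The relative rise in benign lesions sampled is [q / (1 − q)] × f_b / f_W.

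**Results for f_W = 20% and f_b = 40% (a 20-point excess).**

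| q | Difference between the two proportions | Rise in benign lesions sampled |
|---|---|---|
| 0.10 | 0.10 × 20 = 2 points | 22% |
| 0.20 | 0.20 × 20 = 4 points | 50% |
| 0.30 | 0.30 × 20 = 6 points | 86% |

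The middle row in counts: white light 40/200 = 20.0%; blue light adds 50 lesions, 20 of them benign, giving 60/250 = 24.0%. The blue-only figure is 20/50 = 40%, and benign lesions sampled go from 40 to 60. Over q from 0.10 to 0.30 and f_b from 20% to 60%, the difference runs from 0 to 12 points and the rise in benign lesions from 11% to 129%.

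**The denominator matters.** If all 250 sampled lesions are the denominator for both lights, the same counts give 60/250 − 40/250 = 24.0% − 16.0% = 8 points instead of 4.

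**Partial overlap.** Suppose 175 lesions are seen in both lights (25 benign), 25 in white only (15 benign) and 50 in blue only (20 benign). White light is 40/200 = 20.0% and blue light is 45/225 = 20.0%. The difference is zero, while the blue-only figure is 20/50 = 40% and benign lesions sampled rise from 40 to 60.

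**Independence.** If lesions within a patient tend to share benign or malignant status, an interval for either proportion that ignores this will be too narrow. For the difference, the shared lesions generally act in the other direction, so a valid interval has to handle clustering and pairing together. Without lesions per patient or a within-patient correlation, no size can be put on either effect.

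**The case against.** **A zero difference need not conceal anything.** A reader might infer that the endpoint can hide a poor blue-only rate behind equal proportions. When blue light re-finds every white-light lesion, the formula rules that out: the difference is zero only if f_b = f_W. For example, 40/200 for white light and 50/250 for blue light are both 20%, and so are the 10 benign lesions among the 50 added. Benign lesions sampled rise by 25% (40 to 50), but malignant ones also rise by 25% (160 to 200). The proportion is then right and merely is not a count. Equal proportions with a worse blue-only rate need partial overlap, as in the last example above, where blue light misses 15 of the 40 benign white-light lesions. That is possible, but the documents do not predict it.

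**Benefit is not measured only on the increment.** The lesion detection rate by type in 7.2 is a measure for each light at lesion level and a natural counterpart to the false positive proportion, which also answers its stated objective. This stands, and is why the two planned proportions should be kept.

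**The data will exist.** Lesions are recorded under each light (7.4.1, 7.4.2), the primary endpoint already requires blue-only lesions to be identified, and 10.4.2.2 promises detailed tables. The blue-only figure should therefore be derivable. But it is not pre-specified, and a promise of tables does not fix its definition.

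**PUNLMP.** A reader might infer that PUNLMP lesions will count both as detections and as false positives. Section 7.3 defines malignancy, not a false positive, so double counting is only a possibility left by an undefined term.

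**Conclusion.** The point holds as a gap in specification. Under the most natural denominator, with blue light re-finding all white-light lesions, the planned contrast shrinks the blue-only excess by the factor q: a 20-point excess shows as 2 to 6 points for q from 0.10 to 0.30. Neither proportion gives the number of benign lesions, or of patients, sampled only because blue light was added. The denominator and the definition of a false positive are missing, and lesion-level intervals may be too narrow.

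This rests on assumed lesion counts, rates and overlap, and on a denominator that the plan does not state. The documents do not support the inference that the trial's benefit-risk conclusion would be too favourable: they contain no such conclusion and no rule for reaching one. The endpoint is descriptive, so the primary test, its error rate and the 94 patients are unaffected. It is worth settling before database lock, so that the blue-only figure is not chosen after the results are seen.

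**What to change.** Keep the two planned proportions and state their denominator. In sections 7.2 and 10.4.2.2 add:

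- counts and false positive proportions for lesions seen in blue only, in white only and in both lights;
- the number and proportion of FAS patients with at least one blue-only benign biopsy;
- intervals that allow for clustering and pairing within patient, for example by resampling patients, in place of the independence assumption.

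Define a false positive as a sampled lesion whose central diagnosis is none of PUNLMP, CIS, Ta, T1 or T2-4, so that no lesion is both a detection and a false positive. Lesions without a consensus diagnosis are already excluded from analysis by section 7.3.

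The cost is a change of wording and a little more analysis on data already collected. The intervals are likely to be wider, and the blue-light false positive figure may look less favourable.
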